STATISTIC

The results obtained from clinical, instrumental and subjective evaluations will be compared between experimental timepoints and later between treatments.

The hypothesis tests used in the study will have a 95% significance level and the statistical power of these tests will be above 80%.

➤ Study Variables

Primary Variables

- To evaluate the treatment superiority with the Exímia Probiac® product associated with the Epiduo® product use versus placebo use and Epiduo® on the success rate of the participants percentage with a reduction in the total number of inflammatory and non-inflammatory lesions in the facial region.
- To evaluate the treatment superiority with the Exímia Probiac® product associated with the Epiduo® product use versus placebo use and Epiduo® on the success rate of the participants percentage with regression of the IGA scale score to grade 1 or zero.

Secondary Variables

- To compare the treatment with the Exímia Probiac® product associated with the Epiduo® product use versus placebo use and Epiduo® on the response rate of the individuals percentage who had regression of the IGA scale score.
- To compare the treatment with the Exímia Probiac® product associated with the Epiduo® product use versus placebo use and Epiduo® on the perceived efficacy of the volunteer, evaluated through subjective questionnaires.
- To compare the treatment with the Exímia Probiac® product associated with the Epiduo® product use versus placebo use and Epiduo® on the evaluation of dilated pores and inflammatory lesions through photographic records and analysis of the Visia® equipment software.

➤ Statistical Methodology

• Primary Variables data analysis

First, we will perform descriptive analyses of the study variables through frequency tables and descriptive statistics (means, standard deviation, minimum, maximum and quartiles).

The percentage of participants with a reduction in the total number of inflammatory and non-inflammatory lesions, the percentage of participants with regression of the IGA scale score to cured (zero score) or almost cured (score one) will be evaluated through the *z test* for comparison of two proportions. The tested hypotheses will be:

$$H_0: \text{Perci}(P + E) \leq \text{Perci}(E)$$

$$H_a: \text{Perci}(P + E) > \text{Perci}(E)$$

Where Percc is the percentage of participants for each study variable.

• Secondary Variables data analysis

In order to evaluate the individuals percentage who presented regression of the IGA scale score, primarily a data descriptive analysis will be performed and subsequently the evaluation through the z test for two proportions.

Ho: $\text{Perci}(P + E) \leq \text{Perci}(E)$

Ha: $\text{Perci}(P + E) > \text{Perci}(E)$

Where Percc is the percentage of participants for each study variable.

The comparison between treatments of perceived efficacy evaluated through a subjective questionnaire and counting the number of inflammatory lesions and dilated pores will be carried out using the Mann Whitney test, which is the most suitable for evaluating ordinal data from independent samples. The tested hypotheses will be:

Ho: $\text{Medj}(P + E) = \text{Medj}(E)$

Ha: $\text{Medj}(P + E) \neq \text{Medj}(E)$

Where Medj is the median of the results of each study variable.

The results will be considered statistically significant at a significance level of 5% (P value ≤ 0.05). The significance level will be controlled by rejecting the null hypotheses if the p Value is less than or equal to 5%.

For the analysis of pores and inflammatory lesions through the Visia® equipment, the equipment's raw data will be exported regarding the parameters quantification of each participant in their respective experimental time. The Anderson-Darling normality test will be applied to identify the data normality. According to the samples distribution result, it will be checked whether there is a difference between the experimental timepoints:

- Parametric tests - *t-student* for paired data to compare experimental timepoints if the normality hypothesis is not rejected;
- Nonparametric tests - *Wilcoxon* for paired data to compare experimental timepoints and *Mann-Whitney*, in case normality is rejected.

Subsequently, the results will be compared between experimental timepoints and later between treatments.

The results will be considered statistically significant at a 5% significance level (P value ≤ 0.05). The significance level will be controlled by rejecting the null hypotheses if the p Value is less than or equal to 5%.

The data collected in the studies will be evaluated according to the statistical methodology described and primary and secondary study variables, after the participants return from D60, D90 visits and the final visit D180.

➤ Sample Design

The study primary hypothesis is the superiority of the Exímia Probiac® and Epiduo® (P + E) combination in relation to Epiduo (E) in the mean percentage change in the number of inflammatory lesions and in the mean percentage change in non-inflammatory lesions. Below is a sample size calculation for the superiority hypotheses: The hypotheses tested for the superiority study will be:

$$H_0: p_t - p_c \leq \delta$$

$$H_A: p_t - p_c > \delta$$

The sample size in each group was calculated considering the following formula:

$$n = \frac{(p_t(1-p_t) + p_c(1-p_c)) (z_{1-\alpha/2} + z_{\beta})^2}{(p_t - p_c - \delta)^2}$$

Where:

For a 5% significance level

$z_{\beta} = 0,864$ → for 80% test power

p_t is the expected proportion of the test group, 69.23%

p_c is the expected proportion of the control group, 52.50%

δ is the margin of superiority, where we will use 1%

Considering the parameters, the sample size considered in the study will be of 200 participants in each group, totaling 400 participants.

➤ Randomization of treatments

The participant determination who will be part of each treatment is performed randomly.

The codes of the 400 participants were arranged in a column in the MINITAB statistical program, then a random sample of 200 participants was selected. Selected participants will use the Probiac and Epiduo combination and the remaining participants will use Placebo and Epiduo.

To ensure that the study is double-blind, the identification that the participant will receive each product sample will be performed by the sponsor according to the study randomization. The collaborators/research assistants who have contact with the participants, during the execution and dispensing of the products to the participants, do not have access to the type of product being used.

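### The lesion primary is any reduction in total lesions in one section and mean percentage change by lesion type in another, and the planning rates belong to neither

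*SAP*

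**What the plan says.** The SAP describes the lesion primary in three ways.

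- **Study Variables, Primary Variables.** The first primary is superiority on the "success rate of the participants percentage with a reduction in the total number of inflammatory and non-inflammatory lesions". No minimum percentage or count is given and no visit is attached. Statistical Methodology repeats the definition without a threshold and assigns it to a z test "for comparison of two proportions", with a one-sided alternative favouring the combination.
- **Sample Design, opening sentence.** The primary hypothesis is superiority "in the mean percentage change in the number of inflammatory lesions and in the mean percentage change in non-inflammatory lesions". This is a continuous outcome, taken on two lesion counts separately.
- **Sample Design, inputs.** The calculation uses proportions: "p_c is the expected proportion of the control group, 52.50"%, against 69.23% in the test group. Neither rate is linked to a responder definition, lesion type or visit.

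Epiduo is the background in both arms: "Selected participants will use the Probiac and Epiduo combination and the remaining participants will use Placebo and Epiduo". The opening paragraph of the SAP says that the power of the tests will exceed 80%.

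**The concern.** These descriptions are not interchangeable. A participant with one lesion fewer than at baseline counts as a success under the first, adds almost nothing to a mean under the second, and has an unknown status under the third. The other primary in the same list has an explicit cut-off (IGA grade 1 or zero), so the missing cut-off for lesions is not just the document's style.

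Two things are at stake. First, the confirmatory test and the stated hypothesis differ, so a significant z test would not establish what Sample Design says the trial is for. A cut-off supplied after the data are seen would also be open to challenge. Second, the power claim rests on rates near the middle of the scale. If success means any drop and both arms receive an active product, the success rates probably lie higher, where the same relative effect gives a smaller difference in proportions.

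**Working it through.** **Inputs from the SAP.** Expected proportions 0.6923 (test) and 0.5250 (control); margin 0.01 in Sample Design and none in the tested hypotheses; 200 per arm; 5% level; one-sided alternative for the primary z test; z for power given as 0.864; a two-sided quantile (1.96) in the sample-size formula.

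**1. The plan's own figure.** The variance term is 0.6923 × 0.3077 + 0.5250 × 0.4750 = 0.4624. Then n = 0.4624 × (1.96 + 0.864)² / (0.6923 − 0.5250 − 0.01)² = 149.03, so 150 per group. The stated 200 does not follow from the stated inputs. That is a separate matter, and the power figures below use the planned 200.

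**2. What the planning rates would mean under the literal rule.** A control success rate of 52.50% implies that 100 − 52.50 = 47.5% of participants on Epiduo plus placebo show no drop at all in total lesions. This is a poor fit for an active treatment and suggests that the rates come from another definition. That is an inference; the SAP does not say.

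**3. Power at the stated rates.** Power = Φ[(p_t − p_c − z × SE0) / SE1], where SE0 uses the pooled proportion, SE1 uses the separate variances, and z = 1.645. Here SE0 = 0.0488 and SE1 = 0.0481, so Φ[(0.1673 − 1.645 × 0.0488) / 0.0481] = Φ(1.81) = 96.5%. Two-sided at 5% it is 93.2%.

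**4. Power if the control success rate is higher.** The SAP's implied odds ratio is (0.6923/0.3077) / (0.5250/0.4750) = 2.04. Hold it fixed and raise the control rate, which is an assumption. For 90%: the odds of 9 become 9 × 2.036 = 18.32, so p_t = 18.32/19.32 = 0.948. Power is then Φ[(0.0482 − 1.645 × 0.02648) / 0.02637] = Φ(0.18) = 57%.

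| Control any-reduction rate (assumed) | Test rate at odds ratio 2.04 | One-sided power | Two-sided power | One-sided power, constant probit shift of 0.44 |
|---|---|---|---|---|
| 52.5% (SAP) | 69.2% | 96.5% | 93.2% | 96.5% |
| 80% | 89.1% | 81% | 71% | 88% |
| 90% | 94.8% | 57% | 45% | 72% |
| 95% | 97.5% | 37% | 26% | 53% |

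One-sided power drops below 80% once the control rate passes about 80% on the odds-ratio scale, or about 86% on the probit scale.

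**5. A second illustration using the SAP's effect.** Assume that 52.50% and 69.23% are rates of at least 50% reduction and that percentage change is normal. The control mean is then 50 + SD × Φ⁻¹(0.525), and the any-reduction rate is Φ(mean/SD); the test arm is handled the same way.

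| SD (points) | Any reduction, control vs test | One-sided power |
|---|---|---|
| 25 | 98.0% vs 99.4% | 32% |
| 30 | 95.8% vs 98.5% | 49% |
| 40 | 90.5% vs 96.0% | 71% |
| 50 | 85.6% vs 93.4% | 81% |

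**The case against.** The strongest reply is that nobody intended any reduction. The text is short and reads like a translation, and a threshold may stand in the protocol, which is not at hand. The implausibility of 52.50% as an any-reduction rate itself suggests that a cut-off exists. The only rates in the document give power above 90% at 200 per arm, and they could equally describe the other binary primary, IGA 0 or 1.

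Much of this stands. It rules out saying that the sponsor chose a low-power rule. It does not remove the contradiction: a cut-off in the protocol would still leave Sample Design naming mean percentage change as the hypothesis while Statistical Methodology tests a proportion. If the rates are IGA rates, the lesion primary has not been sized at all.

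A reader might infer that the z test loses most of its power because nearly everyone succeeds in both arms. The documents do not support that, since they give no any-reduction rate, mean reduction or SD. One assumed case (Epiduo mean reduction 50%, SD 30%, 10-point advantage) gives 95.2% vs 97.7% and 39% one-sided power, against 92% for a two-sided comparison of mean percentage change. Over assumed means of 30–60% and SDs of 25–45% the ranges are 19–70% and 60–98%. In 13 of those 20 combinations the any-reduction test keeps more than half the power of the mean comparison. Ten points is also a smaller effect, at 0.22–0.40 SD, than the 0.44 SD that the SAP's rates imply, so part of that shortfall comes from the assumed effect and not from the endpoint.

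**Conclusion.** The point holds as a contradiction about the primary variable. The tested endpoint, the stated hypothesis and the sizing rates do not describe the same thing, and this can be read from the SAP without any outside figure. It should be fixed before unblinding because it concerns what the primary analysis is.

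The power consequence is conditional. If any reduction is what is meant, the claim of more than 80% fails once the control success rate passes roughly 80–86%, under a constant odds ratio or probit shift taken from the SAP's rates. The loss is moderate at control rates of 80–90% (one-sided power 57–88%). It exceeds half of the 96.5% only at a control rate somewhere between 90% and 95% on the odds-ratio scale, or between 95% and 97% on the probit scale. Where the true rate lies cannot be read from the SAP.

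**What to change.** Make Study Variables, Statistical Methodology and Sample Design name the same lesion primary, by one of two routes.

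1. **Keep a responder endpoint.** Define success by a stated percentage reduction from baseline at a stated visit, and use that definition in the z test. If 52.50% and 69.23% are lesion-responder rates, give the definition and visit to which they refer. If they are not, say what they are and justify rates for the lesion definition. The SAP lists D60, D90 and D180 and ties none of them to this endpoint, so the visit has to be chosen explicitly.
2. **Make percentage change the primary variable.** Compare the arms with adjustment for the baseline count, state how the two lesion types are handled, and justify the sample size on that variable.

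If both are kept, name one as primary and the other as supportive, so that no unadjusted primary test is added to the two already listed.

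The cost is SAP wording and a restated power figure. No new data are needed.

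### The stated primary hypothesis covers non-inflammatory lesions separately, but the plan tests only a pooled lesion total and gives no between-arm analysis of non-inflammatory lesions

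*SAP*

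**What the plan says.** **Primary lesion endpoint** (Statistical Methodology, Primary Variables data analysis). The variable is "The percentage of participants with a reduction in the total number of inflammatory and non-inflammatory lesions", analysed by a z test "for comparison of two proportions". No size of reduction is required and no condition is set on either lesion type. The other primary variable is "regression of the IGA scale score to cured (zero score) or almost cured (score one").

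**Primary hypothesis** (Sample Design). Here the hypothesis is superiority of the combination "in the mean percentage change in the number of inflammatory lesions and in the mean percentage change in non-inflammatory lesions". The two lesion types appear as two separate quantities.

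**Separate lesion analyses** (Study Variables; Secondary Variables data analysis). The secondary list has a comparison "on the evaluation of dilated pores and inflammatory lesions through photographic records and analysis of the Visia® equipment software". The methods add that "counting the number of inflammatory lesions and dilated pores will be carried out using the Mann Whitney test", with paired tests across timepoints for the Visia data. No variable, hypothesis or test is given for non-inflammatory lesions alone.

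**Descriptive analyses.** The primary section opens with "First, we will perform descriptive analyses of the study variables through frequency tables and descriptive statistics". This covers the study variables, and the non-inflammatory count on its own is not listed as one.

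**The concern.** The hypothesis asks about two lesion types and the primary test answers about their sum. Two consequences follow.

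1. **No answer on non-inflammatory lesions.** Inflammatory lesions have a secondary between-arm comparison and non-inflammatory lesions have none. A conclusion that the combination is superior on non-inflammatory lesions, which is half of the hypothesis in Sample Design, would have no analysis behind it.

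2. **Offsetting inside the total.** Any net fall counts as success, so a participant can succeed on one type while the other gets worse. The more numerous type carries more weight. A significant z test could then be reported as an effect on inflammatory and non-inflammatory lesions when only one type moved.

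The point is separate from whether the endpoint should be a mean or a proportion. If Sample Design were reworded as a proportion, the non-inflammatory component would still be untested.

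**Working it through.** **Step 1. Set the sections side by side.**

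| Quantity | Sample Design hypothesis | Primary test | Secondary test |
|---|---|---|---|
| Inflammatory lesions alone | yes | none | Mann-Whitney between arms; paired tests over time (Visia) |
| Non-inflammatory lesions alone | yes | none | none |
| Total of both | no | z test on proportion with a reduction | none |

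The second row is the gap: a quantity in the hypothesis that no analysis reaches. The third row is the reverse: the quantity tested as primary is not the one hypothesised.

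**Step 2. How offsetting works.** Let I and N be the inflammatory and non-inflammatory counts, with subscript 0 for baseline and 1 for follow-up. Success means I1 + N1 < I0 + N0. If I rises by a fraction r, the participant is still a success when N falls by more than r × I0/N0.

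The SAP gives no baseline counts, so I0 = 20 and N0 = 40 are assumed.

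- Baseline: 20 + 40 = 60. Follow-up: 26 + 30 = 56.
- Inflammatory: (26 − 20)/20 = +30%. Non-inflammatory: (30 − 40)/40 = −25%. Total: (56 − 60)/60 = −6.7%. The participant is a success.
- Threshold: a 30% inflammatory rise is offset once N falls by more than 30% × 20/40 = 15%. With equal baseline counts, the fall needed is more than 30%.

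**Step 3. How common it could be.** This is a simulation of one arm with assumed inputs: baseline 20 and 40, each count multiplied by a log-normal factor with log-SD 0.4, and a range of correlations between the two changes.

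| Assumed median change | Correlation | Successes | Successes with more inflammatory lesions than at baseline |
|---|---|---|---|
| Inflammatory 0, non-inflammatory −26% | 0 | 70% | 40% |
| same | 0.5 | 69% | 32% |
| same | 0.7 | 68–69% | 30% |
| Inflammatory about +10%, non-inflammatory −33% | 0 | 72% | 50% |
| same | 0.5 | 70% | 45% |
| same | 0.7 | 70% | 43% |
| Both about −18% (log-mean −0.2 each) | 0 | 71% | 23% |
| same | 0.5 | 70% | 15% |
| same | 0.8 | 69% | 9% |

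**Step 4. Two arms.** Under the same assumptions, leave the inflammatory median unchanged in both arms. Let the non-inflammatory median fall by about 5% in one arm and 26% in the other. The success proportions are 50% and 70% with independent changes, and 52% and 69% at correlation 0.5. The planning values in Sample Design are 52.50% and 69.23%. An effect of about the planned size can therefore arise from non-inflammatory lesions alone. This shows that it is possible, not that it is likely.

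**The case against.** **A pooled total is a legitimate endpoint.** This stands. It is stated, it can be analysed, and nothing in the SAP makes it an error in itself. The defect is the mismatch with the hypothesis in Sample Design.

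**The plan does look at inflammatory lesions.** This also stands. A reader might infer that the trial cannot say which lesion type responded, but the SAP does not support that: a rise in inflammatory lesions hidden in the total could be seen at arm level in the secondary comparison. Two limits remain. That comparison is described through photographs and Visia software, and the SAP does not say that it uses the same counts as the total. Nor is it linked to the wording of the primary conclusion.

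**The co-primary IGA endpoint does not sum lesions.** True, and it gives a separate view of severity. It is a single global grade, however, and does not show which lesion type changed.

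**The wording may mean the total of each type.** This is possible and would sit closer to Sample Design. The text would then have to say how the two combine into one responder status, which it does not, and non-inflammatory lesions would still have no stated analysis.

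**The large masking shares rest on favourable assumptions.** This stands. The 40% and 50% figures assume independent changes and no inflammatory improvement. When both types fall equally, the share is 9% to 23%. None of these figures is a forecast.

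**The protocol may analyse the components.** It may. But this SAP itself lists the variables and tests and itself names the non-inflammatory change as part of the primary hypothesis, so the inconsistency lies within the one document.

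**Conclusion.** The concern holds as a mismatch between hypothesis and analysis. Sample Design hypothesises an effect on each lesion type, the primary analysis tests what reads most naturally as their sum, and only inflammatory lesions are analysed alone. One of the two hypothesised components therefore has no between-arm result.

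Offsetting within the total is certain as arithmetic, but its frequency is unknown. Under the assumed counts and spread it affects about 9% to 50% of successes, depending on whether inflammatory lesions improve and how closely the two changes are correlated.

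A reader might also infer that any joint claim must require both components to favour the combination. The documents set no such rule, and the mismatch can be repaired without one. The point is worth correcting because the repair is cheap. It does not invalidate the primary endpoint.

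**What to change.** 1. Keep the responder proportion on the total as the primary lesion endpoint, and state explicitly that the total is the sum of the two counts, if that is meant.
2. Add two between-arm analyses of percentage change from baseline at the visit used for the primary endpoint, one for the inflammatory count and one for the non-inflammatory count. Use the same counts that form the total, and report an estimate with a confidence interval for each.
3. Bring the hypothesis in Sample Design and the primary analysis into line, so that each quantity hypothesised has a named test and each primary test has a stated hypothesis.
4. State that the lesion conclusion applies to the total unless the component results are reported alongside it.

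**Cost.** SAP wording and two extra analyses. No new data are needed, because both counts are already required for the total. The downside is that the lesion claim may have to be worded more narrowly if one component does not improve.

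### Both primary success rates are tested without baseline information that must already be recorded; a pre-specified adjusted difference would be more precise at no cost in participants, mainly for IGA 0/1

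*SAP*

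**What the plan says.** Under Study Variables, the SAP lists two primary variables, both success rates. One is the "participants percentage with a reduction in the total number of inflammatory and non-inflammatory lesions in the facial region". The other is the "participants percentage with regression of the IGA scale score to grade 1 or zero".

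Under Statistical Methodology (Primary Variables data analysis), both go to a z test "for comparison of two proportions". The alternative is one-sided, that the combination does better than Epiduo with placebo. No covariate, stratified test or adjusted model is named for these variables or elsewhere in the SAP. The secondary variable, any regression of the IGA score, gets the same z test.

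Under Randomization of treatments, the 400 participant codes were listed, "then a random sample of 200 participants was selected", and the rest form the placebo arm. No stratification by baseline severity is described.

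**The concern.** Both primaries are changes from a starting point, so a baseline lesion count and a baseline IGA grade must exist for every participant who can be scored. The SAP uses them to define success and then leaves them out of the comparison.

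For the IGA primary, baseline is likely to be prognostic because the target is absolute. A participant who starts at grade 2 needs to fall one grade; one who starts at grade 4 needs to fall three. For the lesion primary the argument is weaker. Each participant is measured against their own count, and the SAP states no threshold for what counts as a reduction.

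Where baseline predicts outcome and neither the allocation nor the analysis uses it, the interval for the treatment difference is wider than it needs to be. That is the whole of what is at stake. The choice has to be made in advance, because covariates added after unblinding would be open to challenge.

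**Working it through.** **Inputs from the SAP (Sample Design).** "p_t is the expected proportion of the test group, 69.23"%; control proportion 52.50%; margin 1 point; 5% significance; 80% power; 200 per arm.

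**The plan's own figure.** The SAP's formula with z = 1.960 and its printed 0.864 gives 0.4624 × (1.960 + 0.864)² / (0.1673 − 0.01)² = 149.03, so 150 per arm; with 0.8416 it gives 147. Neither is the stated 200. That is a separate matter. What counts here is the precision at 200 per arm.

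**Precision of the unadjusted test.**
- Variance sum: 0.6923 × 0.3077 + 0.525 × 0.475 = 0.2130 + 0.2494 = 0.4624.
- SE of the difference: √(0.4624/200) = 0.0481.
- Power, one-sided 5%, no margin (the hypotheses under Statistical Methodology): Φ(0.1673/0.0481 − 1.645) = 96.7%.
- Power, two-sided 5%, 1-point margin (as under Sample Design): Φ(0.1573/0.0481 − 1.960) = 90.5%.

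**Assumptions, not in the SAP.** Baseline IGA grades 2/3/4 in 30/55/15% of participants, with three gradients of IGA 0/1 success by grade.

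**Formulas.** R² = Σ w(p − p̄)² / [p̄(1 − p̄)]. Adjustment multiplies the variance of the difference by about (1 − R²). Equivalent gain per arm = 200/(1 − R²) − 200. The R² from each gradient is then applied to the SAP's planned proportions.

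| Success at grade 2/3/4 | p̄ | R² | Fall in SE | Gain per arm | Power, one-sided, no margin | Power, two-sided, 1-point margin |
|---|---|---|---|---|---|---|
| 60/45/30% | 47.25% | 0.0096/0.2492 = 3.9% | 1.9% | 8 | 97.2% | 91.6% |
| 65/45/20% | 47.25% | 0.0209/0.2492 = 8.4% | 4.3% | 18 | 97.7% | 92.8% |
| 80/50/15% | 53.75% | 0.0440/0.2486 = 17.7% | 9.3% | 43 | 98.6% | 95.0% |

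**Chance imbalance.** With 15% at grade 4, the SD of the between-arm difference in that share is √(2 × 0.15 × 0.85/200) = 3.6 points. The error that grade imbalance as a whole adds to the estimated difference has SD √(2 × between-grade variance/200): about 1.0, 1.4 or 2.1 points in the three scenarios. The full SE is 4.8 points and the planned difference 16.7.

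**Smaller true effect (assumed 62.5% against 52.5%).** Variance sum 0.2344 + 0.2494 = 0.4838; SE = √(0.4838/200) = 0.0492. One-sided 5% power is about 65% unadjusted and about 67%, 68% or 72% adjusted.

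**Validity, by simulation.** 100,000 trials per setting, 200 per arm, two equal baseline strata, unstratified draw. With success gaps between strata of 0 to 50 points, the unadjusted one-sided 5% test had size 0.048 to 0.050. A stratum-standardised difference had size 0.049 to 0.052. Its SE fell by about 0.5%, 2%, 5%, 9% and 15% as the gap went from 10 to 50 points.

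**The case against.** The strongest reply is that nothing here is wrong. A two-proportion z test under 1:1 randomisation is valid, it fits binary primaries, and it matches the two-proportion sample size formula. This stands, and the simulated size confirms it.

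The second reply is that the size of the gain is assumed throughout. The grade mix and every gradient are illustrative. Two of the three scenarios average 47.25% success, below the SAP's own control proportion of 52.50%, and the gain of 43 per arm needs a steep gradient that the SAP does not support. The entry range for IGA may stand in the protocol, which was not available for this point. If entry were limited to one grade, adjusting for grade would gain nothing. This also stands.

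The third reply is that power is already high. That is true at the planned rates, where the one-sided gain is at most about 2 points in these scenarios. It is less comforting if the true effect is smaller.

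Two stronger readings are tempting, and the SAP supports neither:
- **That baseline severity largely determines who can succeed.** The SAP gives no figure for this, and even the steepest scenario leaves 82% of outcome variance unexplained by grade.
- **That unstratified allocation with an unadjusted test biases the result.** It does not. Imbalance under randomisation is chance variation, and the unadjusted SE already includes it.

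**Conclusion.** The point holds as an efficiency recommendation. The omission and the likely direction of benefit are clear for IGA 0/1. For lesion reduction the benefit is uncertain. If nearly everyone has some reduction, there is little variance left to explain and a logistic model could be unstable.

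The size rests wholly on how prognostic baseline is, which the SAP does not say. Over an assumed R² of 4% to 18% the gain is modest at the planned effect. It is still worth taking, because it needs no extra participants and the adjusted estimate stays on the scale of a difference in percentages that the SAP tests.

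**What to change.** Amend Primary Variables data analysis before unblinding, as follows:

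- **IGA 0/1:** make the primary analysis a logistic regression on treatment and baseline IGA grade, with baseline total lesion count added. Report the standardised difference in success percentages (the average of model-predicted success under each treatment over all participants), its confidence interval, and a p value of the same sidedness as the stated hypotheses.
- **Lesion reduction:** use the same approach, with baseline total lesion count, where the number of non-responders allows a stable model.
- **Secondary IGA regression variable:** the same approach.
- **Details to fix in advance:** the form in which the lesion count enters the model, the variance method for the standardised difference, and the rule for dropping to the fallback.
- **Unadjusted z test:** keep it as the supportive analysis and as the fallback if the model does not converge.

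A Mantel-Haenszel difference stratified by baseline IGA grade would be a simpler alternative. The cost is a few lines of SAP text and code, with no new data and no change to the sample size.

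### Two primary variables are each tested at 5% with no rule saying whether one or both must succeed, so the plan limits only the per-test error, not the error of the superiority claim

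*SAP*

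**What the plan says.** Under Study Variables, the SAP lists two primary variables, both worded as superiority aims. One is the "participants percentage with a reduction in the total number of inflammatory and non-inflammatory lesions in the facial region"; the other is the percentage "with regression of the IGA scale score to grade 1 or zero". Under Primary Variables data analysis, each is compared between groups by a z test for two proportions, with a directional alternative and a null difference of zero. The hypotheses are defined separately for each variable.

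The opening of the SAP sets one level for all tests: "The hypothesis tests used in the study will have a 95% significance level and the statistical power of these tests will be above 80" (per cent). The 95% is evidently meant as a 5% significance level. The only rejection rule is "The significance level will be controlled by rejecting the null hypotheses if the p Value is less than or equal to 5" (per cent). It appears twice, both times under Secondary Variables data analysis. The primary analysis text has no rule of its own.

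Sample Design describes the primary hypothesis differently, as superiority "in the mean percentage change in the number of inflammatory lesions and in the mean percentage change in non-inflammatory lesions", without IGA. It states "For a 5% significance level", enters that level in the formula as z(1-α/2), and uses one pair of rates with a 1% margin.

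**The concern.** A rule that rejects each null at p ≤ 5% bounds the error of each test. With two primary variables, the error of the overall claim also depends on how the two results are combined, and the SAP does not say how. If one variable succeeds and the other fails, the text cannot settle whether superiority was shown, and the choice could be made after the results are known. Because the SAP says that this rule controls the significance level, a reader may take the overall claim to be protected when only the individual tests are.

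Two other features of the text stop the reader from inferring the rule. The primary hypothesis in Sample Design is not the pair listed under Study Variables. The level is also unclear: the directional tests with p ≤ 5% imply one-sided 5%, while z(1-α/2) implies one-sided 2.5%.

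**Working it through.** **The plan's own figure.** Inputs from Sample Design: p_t = 0.6923, p_c = 0.5250, δ = 0.01, z_β = 0.864, 5% level.

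- Variance term: 0.6923 × 0.3077 + 0.525 × 0.475 = 0.4624.
- n = 0.4624 × (1.960 + 0.864)² / 0.1573² = 149.03, so 150 per group.

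The SAP states 200 per group. That difference is a separate matter. Here it matters only because 200 per group is what is available to pay for a stricter rule.

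**False-claim rate at one visit, neither variable effective.** Let c be the one-sided critical value and r the correlation between the two z statistics. The SAP gives no r, so the range is an assumption.

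- Either suffices: P = 2α − P(both), where P(both) = Φ₂(−c, −c; r).
- Both required: P = P(both).

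| r | P(both), α = 5% | Either, α = 5% | Either, α = 2.5% |
|---|---|---|---|
| 0 | 0.0025 | 0.0975 | 0.0494 |
| 0.5 | 0.0122 | 0.0878 | 0.0454 |
| 0.7 | 0.0196 | 0.0804 | 0.0417 |
| 0.9 | 0.0319 | 0.0681 | 0.0352 |

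Example at r = 0: 2 × 0.05 − 0.05² = 0.0975.

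**Both required, one variable effective and the other null.** The error is then close to that of the single null test. With the effective variable shifted by 0.1673/0.04808 standard errors, it is 0.048 to 0.050 and cannot exceed 0.05.

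**Holm on the two variables, neither effective.** The rate is 0.0494 (r = 0) to 0.0352 (r = 0.9) at an overall 5%, and 0.0248 to 0.0181 at an overall 2.5%.

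**Power under the remedies, 200 evaluable per group.** SE = √(0.4624/200) = 0.04808. Power per variable = Φ((0.1673 − m)/SE − c), where m is the null difference. The tests under Primary Variables data analysis have m = 0; Sample Design uses m = 0.01. So (0.1673 − m)/SE is 3.480 or 3.272.

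| Rule | c | m = 0 | m = 0.01 |
|---|---|---|---|
| One variable at one-sided 0.05 | 1.645 | 96.7% | 94.8% |
| One variable at 0.025 | 1.960 | 93.6% | 90.5% |
| One variable at 0.0125 | 2.241 | 89.2% | 84.8% |
| Both at 0.05, r = 0 | 1.645 | 0.9667² = 93.5% | 0.9481² = 89.9% |
| Both at 0.025, r = 0 | 1.960 | 0.9357² = 87.5% | 0.9051² = 81.9% |

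The joint figures assume that both variables have the SAP's rates. Positive correlation raises them.

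**The case against.** The strongest reply is that the inflation is conditional. Nowhere does the SAP say that success on either variable suffices, and if both are required the error is at most 5%. Sample Design even joins its two lesion components with the word *and*, which can be read as a joint claim. This stands as a limit on the point: an unstated rule has been shown, not a failure of error control. The *and* does not settle the matter, because that sentence omits IGA.

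A second reply is that the protocol, which is not at hand, may define the success criterion. It may. But the SAP takes up error control itself and states how the level is controlled, so the objection is to a stated rule that does not reach the claim, not to silence.

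Third, the rejection rule sits under the secondary variables. That is so, but the opening sentence applies one level to all tests and no other rule is offered for the primaries.

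Fourth, on the one-sided 2.5% reading the either-variable rate stays below the 5% that the SAP states. That is correct. The excess over 5% arises only on the one-sided 5% reading.

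A reader might also infer more: that the SAP allows a claim from any of several visits, since it has data evaluated for the "primary and secondary study variables, after the participants return from D60, D90 visits and the final visit D180", or that there are three primary claims once the two lesion components are added to IGA. The documents support neither. The timing sentence says when data are evaluated, not which visit can carry a claim. The three-variable set is a hybrid that no section states. Error rates built on either would describe designs that the SAP does not contain.

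**Conclusion.** The point holds in a limited form. The SAP fixes a per-test threshold for two primary variables and leaves open how they combine into a superiority claim. On the one-sided 5% reading, an either-variable rule could nearly double the false-claim rate. On the one-sided 2.5% reading it would exceed 2.5% but not 5%. A both-required rule would inflate nothing. The sizes rest on the assumed correlation range and on a single deciding visit. The existence of the gap rests on neither. It should be fixed before the data are analysed, and it does not call the design itself into question.

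**What to change.** 1. Reconcile the primary variables under Study Variables with the primary hypothesis in Sample Design, so that there is one primary set.
2. State one overall one-sided level, 5% or 2.5%, and use it in both the analysis and the sample-size text.
3. Name one deciding visit, or cite the protocol if it already names one.
4. State the success rule at that visit: both primaries must succeed, each at the stated level; or a fixed sequence; or Holm. Holm on two variables starts at 0.025 for an overall 5% and at 0.0125 for an overall 2.5%. If the protocol already holds the rule, cite it.

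This is a change of wording. The price is a joint requirement or a stricter first threshold. At the SAP's rates and 200 evaluable per group, the tightest option (both required at 2.5%, uncorrelated, 1% margin) still has 81.9% power, and with the zero margin of the stated primary tests it has 87.5%. No added enrolment follows from these figures. Two cautions apply: the SAP does not say which primary variable its rates describe, so power for the other is unknown; and its promise of more than 80% is made per test, so setting joint power against it is a stricter standard than the SAP sets itself.
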